## APPENDIX C SLIT-LAMP EXAM RATINGS

### A. Ratings of Aqueous Cells and Flare

For consistency across study sites, the SUN (Standardization of Uveitis Nomenclature) Working Group Grading Scheme is to be used for grading of anterior chamber cells and flare as reported in: Standardization of uveitis nomenclature for reporting clinical data. Results of the first international workshop; The standardization of uveitis nomenclature (SUN) working group. Am J Ophthalmol 2005;140:509-516.

#### CELLS

Grade	Cells in Field (Field is a 1x1 mm slit beam)
0	<1
0.5+	1 - 5
1+	6 - 15
2+	16 - 25
3+	26 - 50
4+	>50

#### FLARE

Grade	Description
0	None
1+	Faint
2+	Moderate (iris and lens details clear)
3+	Marked (iris and lens details hazy)
4+	Intense (fibrin or plastic aqueous)

### B. Ratings of Corneal Edema

Corneal edema should be classified according to the haziness of the epithelium, the number of microcysts observed, and the clouding of the stroma.

Amount	Grade	Description
None	0	Normal transparency: a. No epithelial or sub-epithelial haziness b. No microcysts c. No stromal cloudiness
Trace	+1	a. Barely discernible localized epithelial or sub-epithelial haziness, and/or b. 1 to 20 microcysts, and/or c. Barely discernible localized stromal cloudiness
Mild	+2	a. Faint but definite localized or generalized epithelial, sub-epithelial or stromal haziness/cloudiness, and/or b. 21-50 microcysts
Moderate	+3	a. Significant localized or generalized epithelial, sub-epithelial or stromal haziness/cloudiness and/or b. 51-100 microcysts
Severe	+4	a. Definite widespread epithelial or stromal cloudiness, giving dull glass appearance to cornea or numerous coalescent bullae (please note the number and location of bullae), and/or b. >100 microcysts or bullae, and/or c. Numerous striae (please note the number and location of striae or folds)

### C. Posterior Capsule Striae Grading Scale

The following five-point grading scale is to be used for rating striae in the posterior capsule:

Amount	Grade	Description
None	0	None
Trace	+1	One detectable, barely noticeable striae
Mild	+2	One or two prominent striae
Moderate	+3	Three or more prominent striae, but visibility of retina is not impacted
Severe	+4	Three or more prominent striae affecting visualization of retina

### D. Posterior Capsule Opacification Grading Scale

Below is the five-point grading scale to be used for PCO determination:

Amount	Grade	Description
None	0	Normal posterior capsule with no area of opacity. Red reflex bright.
Trace	+1	Some loss of transparency involving the posterior capsule. Red reflex fairly bright
Mild	+2	Mild loss of transparency with cloudiness extending through most of the posterior capsule. There may be a few Elschnig's pearls in the posterior capsule. Red reflex mildly diminished.
Moderate	+3	Moderate loss of transparency with difficulty visualizing the retina. There may be multiple Elschnig's pearls in the posterior capsule. Red reflex markedly diminished.
Severe	+4	Posterior capsule very opaque with inability to view the retina. The posterior capsule may have confluent Elschnig's pearls and fibrous scarring. Red reflex barely visible.

### E. IOL Glistenings

Use the following scale to grade IOL glistenings, using a slit beam 2.0 mm wide and 10.0 mm long:

Amount	Grade	Description
None	0	No glistenings visible
Rare	+0.5	<10 glistenings visible
Trace	+1	10-19 glistenings visible
Mild	+2	20-29 glistenings visible
Moderate	+3	30-39 glistenings visible
Severe	+4	≥ 40 glistenings visible

## APPENDIX D ADVERSE EVENT AND COMPLAINT REPORTING INSTRUCTIONS

All adverse events and complaints related to using AMO products must be reported to AMO.

### ALL ADVERSE EVENTS AND COMPLAINTS:

For events that are not considered serious and/or related to the study device:

1. Record the event and/or complaint on the case report form that corresponds to the visit during which awareness of the event occurred. Additionally, a complaint may be reported via a telephone call to AMO.
2. Complete the case report form in AMO's data management system in a timely manner, preferably within 1 week of the study visit.

### SERIOUS ADVERSE EVENTS OR DEVICE DEFICIENCIES THAT MAY HAVE LED TO A SERIOUS EVENT

In the event of a serious event (i.e., life- or sight-threatening incident), or a device deficiency that may have led to a serious event, the investigator shall:

1. Notify AMO immediately (no more than 48 hours after learning of the event) as follows:
  - a. Contact the following AMO personnel by phone or email:  

- a. If a serious adverse event, also complete the Serious or Device Related Adverse Event Form in AMO's data management system.

### NON-SERIOUS, DEVICE-RELATED EVENTS

For events that are not considered serious but are believed related to the study device (ADEs):

1. Complete the Serious or Device Related Adverse Event Form
2. Submit the completed Serious or Device Related Adverse Event Form to AMO within a timely manner.

## 1. Introduction

This document summarizes the statistical methods to be implemented during the analysis of data for the post-approval study of the TECNIS® Toric IOL models ZCT450, ZCT525 and ZCT600. The purpose of this study is to evaluate the rate of severe visual distortion with these lenses in clinical practice. This study will be a prospective, multicenter, bilateral, open-label clinical investigation. Subjects are to be bilaterally implanted with at least one eye having a ZCT450, ZCT525 or ZCT600 IOL and the fellow eye having a high cylinder toric IOL (models ZCT300 to ZCT600).

The key timeframe for analysis will be the six month visit. The primary endpoint for this study is the rate of severe visual distortions defined as the proportion of subjects who report a severe visual distortion under overall circumstances at 6 months for any of the following 5 visual distortion items of interest:

- lines that slant, tilt, split or separate
- flat surfaces appearing curved
- objects appearing further away or closer than they actually are
- objects appearing to have a different size or shape
- physical discomfort related to vision

For the primary endpoint, severe visual distortions will be assessed using the overall circumstance reply at the 6 month visit. For the primary endpoint, the frequency and proportion of subjects reporting one or more of these items as severe will be used to determine the rate of severe visual distortions

Results from individual visual distortion items on the PRVDQ questionnaire will also be reported for the overall circumstance and the with and without correction circumstances.

Other endpoints include: refraction results, uncorrected and corrected distance visual acuity, medical/lens findings and adverse events.

## 2. Analysis Populations and Data Conventions

### 2.1 Analysis Population

The primary analysis population will be all bilaterally implanted subjects having available data at the six month visit. In addition, data for severe visual distortions (based on the 5 defined items) will also be reported for all subjects including bilateral subjects and those with only one eye implanted and the fellow eye having phakic status, a cataract, or another IOL. If a subject does not have overall severe visual distortion data available at the six month visit (or had a repositioning procedure or IOL removal performed) then data for the endpoint will be carried forward from the most recent postoperative visit (for general missing data) or the postoperative visit prior to the IOL repositioning or removal. If a subject had an IOL repositioning/removal procedure and did not have visual distortion data available prior to the procedure, then the subject will be considered to have had severe visual distortions for the primary endpoint. For overall severe visual distortions based on the 5 defined items, an additional analysis population will be evaluated that includes all subjects with last observation carried forward for missing data as described above as well as use of data imputation for subjects with no available questionnaire data at any time point. Imputation for those with no questionnaire data will be performed using multiple imputation techniques as described in Little and Rubin and implemented using the MI and MIANALYZE procedures in SAS® (Version 9.2 or later

version if available). Additional sensitivity analyses will be performed including worst-case analysis where all missing visual distortion data (using the 5 defined items) will be treated as having a severe visual distortion and best-case analysis where missing data is treated as having no severe visual distortion. If more than 10 percent of visual distortion data (using the 5 defined items) are missing then a tipping point analysis will also be evaluated.

Data will typically be reported for all bilateral subjects, however, for some analyses, such as the overall visual distortion endpoint, data will also be reported by IOL group. Subjects who have a lower cylinder IOL in one eye (e.g. ZCT300) and a higher cylinder IOL in the fellow eye (e.g. ZCT450) will be placed in the higher cylinder group for analysis when reporting data by subject.

When reporting data by eye (refraction, monocular visual acuity, complications), the primary eye will be the eye with the higher cylinder IOL (or the first eye if the same IOL is implanted in both eyes). The data will be reported separately for the fellow eye.

Refraction, visual acuity and medical and lens findings for primary and fellow eyes will be reported separately for those eyes with a ZCT450 to ZCT600 IOL and those with a ZCT300-ZCT400 IOL. Adverse events will be reported for all primary and fellow eyes in the study and will indicate the IOL implanted.

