If a subject reported a severe visual distortion in the questionnaire or experienced a serious or device-related adverse event at any unscheduled study visit, uncorrected distance visual acuity, best corrected distance visual acuity, manifest refraction, keratometry, intraocular pressure and biomicroscopic slit-lamp examinations will also be performed.

A 1-year examination will be required only if the subject reports a severe visual distortion at the 6-month examination or experienced an IOL repositioning procedure (due to IOL misalignment during the study).

If a serious or device-related adverse event occurs at or prior to the 6-month visit, details of the event will be collected at the time of the event using an adverse event form. If the adverse event results in an IOL repositioning procedure due to misalignment, the questionnaire should be administered prior to the procedure to collect information regarding visual distortions. Keratometry and toric IOL axis measurements will be performed prior to the repositioning procedure to collect data regarding the IOL misalignment.

A chart summary of all examination procedures required at each study visit is provided in Appendix A.

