#### SUBJECT DISCONTINUATION

Subjects will be discontinued from the study if the study lens is removed or if the subject dies. Subjects will be considered "lost-to-follow-up" from the study only if irretrievably lost for unavoidable reasons such as: subject moved/unable to locate, subject uncooperative/refuses further study participation, subject ill/unable to travel. The site shall document at least three attempts (phone calls/emails and/or letters) to locate lost-to-follow-up subjects and the investigator should notify AMO prior to exiting a subject from the study. If a subject is exited from the study, the investigator will, if at all possible, have the subject return for a final study visit. In the event of subject relocation, efforts must be made by the investigator to secure follow-up information (i.e., slit-lamp findings and general visual acuity, etc.) from the subject's new physician.

If a subject is exited early from the study, the investigator will complete an Exit Case Report Form indicating the reason for study exit. In the event of a lens removal or other serious adverse event, the subject may be exited from the study; however, efforts must be made by the investigator to follow the subject until resolution of the adverse event.

Note: A subject may be exited from the study if complications occur during the first-eye surgery and the planned study lens is not implanted; however, the eye will be followed until the resolution of the complication prior to exiting the subject from the study. If a complication occurs during the second-eye surgery and the planned study lens is not implanted in the second eye, the subject is to be followed according to the protocol for

the first eye (although data may be analyzed separately), and the second eye will be followed for safety until resolution of the complication.

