### 20.2 ANALYSIS POPULATION

For the primary endpoint and most visual distortion endpoints, the primary analysis population will be all bilaterally implanted subjects having available data at the 6-month visit. Data will also be reported for all subjects including bilateral subjects and those with only one eye implanted (having a phakic lens, a cataract or other IOL in the fellow eye). Data will also be reported by IOL group. If a subject does not have overall severe visual distortion data available at the 6-month visit (or had a repositioning procedure or IOL removal performed) then data for this endpoint will be carried forward from the most recent visit (for general missing data) or the visit with data taken prior to the IOL

repositioning or removal. If a subject had an IOL repositioning/removal and no questionnaire data prior to the procedure, then the subject will be considered to have had a severe visual distortion for this endpoint. An additional analysis will be performed for the primary endpoint using multiple imputation techniques for those with no questionnaire data available. Sensitivity analyses such as worst-case and best-case will also be performed.

Refraction, visual acuity, medical/lens findings, axis evaluation and adverse events will be reported for primary eyes (those having the higher cylinder IOL or the first eye implanted if the same IOL is implanted in both eyes) and fellow eyes. Data will be reported separately for ZCT450-ZCT600 eyes and ZCT 300-ZCT400 eyes.

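### The primary population requires 6-month data, yet the same paragraphs give primary values to subjects who may lack it, and nothing says which rule sets the denominator

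*SAP*

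**What the plan says.** **Population.** SAP 2.1: "The primary analysis population will be all bilaterally implanted subjects having available data at the six month visit". Protocol 20.2 agrees: "the primary analysis population will be all bilaterally implanted subjects having available data at the 6-month visit".

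**Values for subjects outside that description.** A later sentence of the same SAP paragraph opens "If a subject does not have overall severe visual distortion data available at the six month visit (or had a repositioning procedure or IOL removal" and goes on to carry forward an earlier postoperative value. For a repositioning or removal with no earlier distortion data, "then the subject will be considered to have had severe visual distortions for the primary endpoint". Protocol 20.2 gives matching rules.

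**A further population.** The SAP then says "an additional analysis population will be evaluated that includes all subjects with last observation carried forward for missing data as described above", with multiple imputation added for subjects who have no questionnaire at any time. Worst-case and best-case analyses follow, and a tipping-point analysis if more than 10% of the data are missing.

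**Lens removal.** Protocol 11.8, under subject discontinuation: "Subjects will be discontinued from the study if the study lens is removed or if the subject dies". The next paragraph of that section is weaker: "In the event of a lens removal or other serious adverse event, the subject may be exited from the study".

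**The concern.** The population sentence admits subjects by whether they have 6-month data. The rules that follow exist largely for subjects who do not. For the two to work together, a carried-forward or assigned value has to count as available 6-month data, and neither document says that it does. By placing carry-forward inside an additional population, the SAP gives some support to the view that the primary set is observed cases only.

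Lens removals are the exposed group. A subject discontinued at removal before 6 months would normally have no 6-month questionnaire. For a repositioning due to misalignment, Protocol 11.1 says "the questionnaire should be administered prior to the procedure to collect information regarding visual distortions"; there is no matching instruction for removal. At 1 month the questionnaire is given only after a spontaneous report or before a repositioning (Protocol 11.6). Removals are therefore the cases most likely to need the severe-by-default rule, and a literal population sentence leaves them out.

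The endpoint is a safety rate in an open-label, single-arm study. If the denominator is not settled in writing, it can be settled after the results are known.

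**Working it through.** **1. The plan's own figure.** Inputs from SAP 7 and Protocol 20.6: N = 80, rate 0.025, half-width 0.05, two-sided 95% interval. Taking half the length of the Clopper-Pearson interval at each count x out of 80:

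| x | half-width |
|---|---|
| 0 | 0.0225 |
| 1 | 0.0337 |
| 2 | 0.0422 |
| 3 | 0.0490 |
| 4 | 0.0547 |

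Counts 0 to 3 qualify, and P(X ≤ 3) for Binomial(80, 0.025) is 0.859. The stated 86% reproduces; the Wilson interval gives the same value. The figure assumes 80 evaluable subjects. Protocol 11.8 anticipates up to 10% loss at 6 months. If the literal restriction leaves 80 × 0.9 = 72, only counts 0 to 2 qualify and the probability is 0.731.

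**2. The two readings, subject by subject.**

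| Bilateral subject | Only observed 6-month data count | Carried or assigned values also count |
|---|---|---|
| Questionnaire at 6 months, no procedure | in | in |
| Repositioned, with 6-month data | in; pre-procedure value, or severe if none | the same |
| Ordinary missing, earlier postoperative questionnaire | out | in, carried value |
| Lens removed, no 6-month data, earlier questionnaire | out | in, pre-removal value |
| Lens removed, no questionnaire | out | in, severe |
| No questionnaire, no procedure | out | out; imputation only |

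The readings differ in rows 3 to 5.

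**3. Direction.** Let n be the bilateral subjects with a value under the wider reading, x the other severe reports, and r the removals that would be assigned severe. The rate is x/(n − r) with them excluded and (x + r)/n with them counted. Cross-multiplying, (x + r)(n − r) − xn = r(n − r − x), which is positive whenever any remaining subject is not severe. Excluding such removals therefore lowers the rate.

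**4. Size.** The documents give no removal rate, so r = 1 to 3 is assumed, each without an earlier questionnaire. Take n = 80, x = 80 × 0.025 = 2, and data for everyone else. Clopper-Pearson 95% intervals:

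| r | Excluded | Counted as severe |
|---|---|---|
| 1 | 2/79 = 2.5% (0.3–8.8%) | 3/80 = 3.8% (0.8–10.6%) |
| 2 | 2/78 = 2.6% (0.3–9.0%) | 4/80 = 5.0% (1.4–12.3%) |
| 3 | 2/77 = 2.6% (0.3–9.1%) | 5/80 = 6.3% (2.1–14.0%) |

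With n = 72, x = 2 and one removal: 2/71 = 2.8% (0.3–9.8%) against 3/72 = 4.2% (0.9–11.7%). With n = 80 and only one other severe report, it takes two removals to carry the upper limit past 10%: 1/78 has upper limit 6.9%, and 3/80 has 10.6%.

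**The case against.** The best answer is that a specific rule governs a general one. The severe-by-default rule is written expressly for the primary endpoint and names removals. Applying the population sentence literally would cancel it for many of the cases it describes. Protocol 20.2 reserves the word additional for multiple imputation, and the SAP sentence on the extra population can be read as adding imputation to a carry-forward already in use. This is a reasonable reading, and may well be the intended one.

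Other points also stand:

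- Repositioned subjects stay in follow-up, and the rules work for those with 6-month data.
- A removal need not leave a subject without data. Protocol 11.8 also makes exit optional and asks for a final visit where possible, and a subject who spontaneously reported a listed distortion, or blurred or hazy vision, from 1 month on should have had the questionnaire.
- The carry-forward/imputation set, the worst-case analysis and the adverse event tables would bring excluded cases into view.

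A reader might infer that the plan deletes lens removals from the primary endpoint. The documents do not support that: they contain an unresolved conflict, and one side of it keeps removals in. A reader might also infer that one removal decides whether the study succeeds. SAP 4.1 makes the aim estimation, and no test or success rule is attached to the 10% in the clinical hypothesis.

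These points limit the effect to the headline number. They do not say which number that is: sensitivity analyses report alternatives to a primary estimate and cannot select it.

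**Conclusion.** The concern holds as a conflict between stated rules. Under the literal reading, removals without 6-month data and other subjects without a 6-month questionnaire leave the primary rate. The expected bias is downward: removals with no earlier questionnaire would have counted as severe, and postoperative questionnaires before 6 months come mainly from subjects who had already reported symptoms. A subject whose carried value is not severe would pull slightly the other way.

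At the planning rate, one removal without a questionnaire moves the estimate from 2.5% to 3.8% and the upper limit from 8.8% to 10.6%. This rests on assumed counts. The 10% is a reference point from the clinical hypothesis only. The sample-size statement is correct for 80 evaluable subjects. The matter should be settled before the analysis, since either denominator can be defended from the present text.

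**What to change.** - In SAP 2.1 and Protocol 20.2, define the primary population as all bilaterally implanted subjects with an observed, carried-forward or rule-assigned 6-month outcome. All bilaterally implanted subjects would be too wide, because it admits subjects who have no value under any rule.
- State that both the repositioning/removal rule and the carry-forward rule feed the primary analysis.
- Keep subjects with an observed 6-month questionnaire as a supportive analysis.
- Keep multiple imputation, for subjects with no questionnaire data, as the additional analysis, and reword the SAP sentence so that only imputation is what the additional population adds.
- Reconcile the two statements in Protocol 11.8 on whether a subject is discontinued after lens removal. Which one applies is for the sponsor to decide.

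The cost is wording in three places, with no new data collection. The reported rate may be slightly less favourable.

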## 11. STUDY PLAN

### 11.1 OVERVIEW

This study will be conducted in accordance with U.S. Code of Federal Regulations, the Declaration of Helsinki, ISO 14155 and all other applicable laws and regulations. The study will not begin until regulatory and IRB approvals have been obtained

This study is a prospective, multicenter, bilateral, non-randomized, open-label, clinical study conducted at up to 20 US sites. Subjects will be bilaterally implanted with high cylinder TECNIS Toric IOLs, Models ZCT300-ZCT600 in both eyes with at least one eye implanted with a Model ZCT450, ZCT525 or ZCT600. The eye with the highest toric power lens will determine the lens group. Second-eye surgeries are to be performed within approximately 1 month (no more than 60 days) of the first-eye surgery, as second-eye cataract surgeries are typically performed within 2 months of the first-eye surgery. Subjects will be examined postoperatively at 1 and 6 months following the second-eye surgery. If a subject requires a lens repositioning procedure due to IOL misalignment or if a subject reports a severe visual distortion at 6 months, the subject will undergo a final visit at 1 year. Additional visit schedule details are provided in Section 11.2 Visit Schedule.

At the 1-month visit, a spectacle and/or contact lens prescription will be offered to each subject. Postoperative procedures will include uncorrected and best corrected visual acuities, manifest refraction, intraocular pressure and biomicroscopic slit-lamp examination. In addition, if the subject has a spontaneous report of any of the 5 visual distortion items of interest or of blurred or hazy vision, the questionnaire will be administered and keratometry and toric IOL axis measurements will be performed.

At the 6-month visit, the postoperative procedures will include a subject questionnaire for determination of visual distortions, keratometry, uncorrected and best corrected visual acuities, manifest refraction, intraocular pressure and a biomicroscopic slit-lamp examination for determination of toric IOL axis position and for any adverse events.

If outside of a scheduled study visit, a subject has a spontaneous report of; 1) any of the 5 visual distortion items of interest or 2) blurred or hazy vision at one month postoperatively or later, the PRVDQ questionnaire will be administered and keratometry and toric IOL axis measurements will be performed. Exam details will be documented on an unscheduled visit form.

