## **18. RISK ANALYSIS**

### **POTENTIAL RISKS AND RISK MANAGEMENT**

#### ***RISKS OF THE TECNIS TORIC IOLS***

The TECNIS Toric IOLs are designed to provide improved uncorrected distance vision, reduction in residual refractive cylinder, and increased spectacle independence for distance; however, glasses may still be needed to improve distance vision and/or to have useful vision for intermediate or near tasks. In addition, rotation of the TECNIS Toric IOLs away from its intended axis can reduce its astigmatic correction. Misalignment greater than 30° may increase postoperative refractive cylinder. If necessary, lens repositioning should occur as early as possible prior to lens encapsulation. These risks are not unlike other lenses of this kind. As the TECNIS Toric ZCT450, ZCT525 and ZCT600 IOLs have higher amounts of cylinder correction, there may be an increased risk of visual distortions arising from misalignment.

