### **20.3 PRIMARY ENDPOINT**

The primary endpoint for this study is the rate of severe visual distortions (under overall circumstances) as measured by the 5 visual distortion items of interest in bilateral subjects at 6 months. The frequency, proportion and a two-sided 95% confidence interval will be reported for this endpoint. The frequency and proportion of subjects reporting one or more of these items as severe will be used to determine the rate of severe distortions.

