### 4.2 Other Visual Distortion Endpoints Related to Severe Visual Distortions

In addition to the above analysis related to the primary endpoint, other analyses will also be performed for severe visual distortion rates (based on the 5 defined items) in the overall circumstance and will include the frequency and proportion with severe visual distortions. Severe visual distortion data for the overall circumstance will be reported by the IOL group for bilateral subjects. The severe visual distortion rate will also be reported for all subjects enrolled in the study including bilateral subjects and those implanted in one eye (with a cataract, phakic condition or having another IOL (i.e. not a ZCT300-ZCT600 IOL) in the fellow eye). A trend analysis will be performed by plotting the severe visual distortion rate by increasing toric IOL cylinder power. To examine within subject changes for visual distortions (based on the 5 defined items in the overall circumstance) for subjects with data at both the 1 month and 6 month visits, the frequency and proportion will be reported for the following categories: those with severe distortions at both visits, those with severe distortions only at 1 month, those with severe distortions only at 6 months and those with no severe distortions at 1 month or 6 months. In addition, for subjects with severe visual distortions (based on the 5 defined items) at any time point, data will be provided indicating when the severe visual distortions were reported and the status at 6 months. Results for severe visual distortions will also be reported by investigational site. Any unusual patterns due to site will be noted (i.e. all severe visual distortions at 1 or 2 sites) and further analyses performed to address any site issues. Details on age, sex, race and cylinder will be reported for subjects experiencing severe visual distortions.

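### The rules that fill the bilateral 6-month endpoint do not require the source questionnaire to follow the second-eye implant

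*SAP*

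**What the plan says.** **Endpoint and population.** Protocol 20.3 defines the rate "as measured by the 5 visual distortion items of interest in bilateral subjects at 6 months". SAP 2.1 states: "The primary analysis population will be all bilaterally implanted subjects having available data at the six month visit". One-eye subjects enter only the separate all-subjects result, where SAP 4.2 adds "those implanted in one eye (with a cataract, phakic condition or having another IOL" in the fellow eye.

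**Rules that fill the endpoint.** Under SAP 2.1 the value is "carried forward from the most recent postoperative visit (for general missing data) or the postoperative visit prior to the IOL repositioning or removal". Protocol 20.2 drops the word *postoperative*: if the 6-month value is unavailable, "then data for this endpoint will be carried forward from the most recent visit (for general missing data"), and after a repositioning or removal it comes from an earlier visit with data. A subject with such a procedure who "did not have visual distortion data available prior to the procedure, then the subject will be considered to have had severe visual distortions" is the SAP's default case.

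**Timing.** Protocol 11.1 says: "Second-eye surgeries are to be performed within approximately 1 month (no more than 60 days) of the first-eye surgery". Table 4 counts the 1- and 6-month visits from the second implant. Unscheduled visits (Protocol 11.7) are not tied to either surgery. A questionnaire is given there on a spontaneous distortion complaint and before a repositioning. On the risk of rotation, Protocol 18 says that, if necessary, "lens repositioning should occur as early as possible prior to lens encapsulation".

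**The concern.** The documents treat the one-eye state as different from the bilateral state: it has its own analysis, and the scheduled visits are counted from the second implant. The fill rules do not carry that distinction. *Postoperative* in the SAP names no eye, and *most recent visit* in the Protocol is not even limited to after surgery.

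Between the surgeries the unoperated eye has a cataract and, by the inclusion criteria, at least 2.00 D of keratometric cylinder. The endpoint items include altered size or shape of objects and visual discomfort. A reply from that period need not reflect vision with both study lenses in place. Neither document fixes which eye is operated first, so such a reply may even precede the implantation of any ZCT450-ZCT600 lens. The subject would still be analysed in the higher-cylinder group.

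With about two events expected in 80 subjects, one changed score is visible in the result. A rule chosen after the replies are known would be post hoc.

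**Working it through.** **1. The plan's own figure.** Inputs from SAP 7: n = 80, rate 0.025, 95% interval, half-width 0.05. With an exact (Clopper-Pearson) interval the half-width is 4.90 points at 3 events and 5.47 at 4, so the target is met for X ≤ 3. P(X ≤ 3 | 80, 0.025) = 0.859, which reproduces the stated 86%. The exact interval is therefore used below.

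**2. Which questionnaires the wording admits as a source.**

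| Occasion | Both eyes implanted? | SAP 2.1 | Protocol 20.2 |
|---|---|---|---|
| Preoperative (all subjects) | No | Not for carry-forward | Admitted as worded |
| Unscheduled visit between surgeries | No | Admitted | Admitted |
| Before a first-eye repositioning between surgeries | No | Admitted | Admitted |
| 1 month (only on a spontaneous complaint or before repositioning) | Yes | Admitted | Admitted |

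The route is open in time. The one-month limit in Protocol 11.1 and 11.7 does not say which surgery it counts from. Even if it covers every complaint and counts from the first eye, about days 30 to 60 can still precede the second surgery. The questionnaire before a repositioning has no such limit.

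**3. What each rule then does.**

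- *General missing data.* The 1-month questionnaire is conditional, so a between-surgery reply can be a subject's last postoperative reply before 6 months, and it is carried forward. Whether it reaches the primary analysis is unclear, because the population sentence asks for available 6-month data.
- *Repositioning.* The rule applies whether or not a 6-month reply exists. A one-eye reply given before the procedure therefore replaces an observed bilateral reply inside the stated primary population.
- *Direction.* One-eye severe and 6-month not severe adds an event. One-eye not severe and 6-month severe removes one.
- *Planned sensitivity analyses.* Multiple imputation, worst case, best case and tipping point all address missing data. None shows an observed reply that was replaced.

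**4. Size of one changed score.** 1/80 = 1.25 points, half of the planning rate of 2.5%. Exact 95% intervals:

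| Events/80 | Rate | 95% CI |
|---|---|---|
| 1 | 1.25% | 0.03-6.77% |
| 2 | 2.50% | 0.30-8.74% |
| 3 | 3.75% | 0.78-10.57% |
| 4 | 5.00% | 1.38-12.31% |

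If one subject is scored severe from the one-eye state and the other 79 follow the planning rate, P(half-width ≤ 0.05) = P(X ≤ 2 | 79, 0.025) = 68%. With two such subjects it is P(X ≤ 1 | 78, 0.025) = 42%.

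**5. Frequency (assumed; the documents give none).** Suppose 1-3% of first eyes are repositioned and 50-80% of those before the second surgery. The share is then 0.5% to 2.4%, the expected number is 80 × share = 0.4 to 1.9, and the chance of at least one is 1 − (1 − share)^80 = 33% to 86%. These count repositionings, not changed scores. If the two replies differ in 25-50% of them (also assumed), the expected number of changed scores is 0.1 to 0.96, and the chance of at least one is 10% to 62%.

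**The case against.** **The pre-procedure score looks deliberate, and this is a safety study.** Protocol 11.7 asks for the questionnaire before repositioning so that distortion from misalignment is captured. A rotated first lens that causes severe distortion and a second procedure is an event of interest. Scoring by the 6-month reply whenever the procedure precedes the second implant would let surgical scheduling decide: with eye 2 on day 35, procedures on days 34 and 36 would be scored differently. This stands. It is why these subjects should not simply leave the headline rate, and why both scorings are needed.

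**Disclosure partly exists.** SAP 4.2 will show when severe distortions were reported and the status at 6 months, and repositioning rates are a separate endpoint. This also stands in part. However, the subject listing in SAP Appendix I has no surgery or procedure dates, and disclosure does not settle how the headline is scored.

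**Readings that go further than the documents.**

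- *A repositioning without a questionnaire is automatically severe.* A questionnaire is required before repositioning for misalignment, so its absence would be a deviation. The preoperative questionnaire may also count as earlier data, so even then the default is ambiguous.
- *The general-missing route inflates the primary rate.* It may fall outside the primary population, and Protocol 11.8 asks for every effort to bring back subjects with an early severe report.
- *Removal poses the same problem.* It matters less, because Protocol 11.8 discontinues a subject whose study lens is removed.

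**Conclusion.** The gap is real in both documents. It is clearest for a first-eye repositioning before the second surgery, where a one-eye reply replaces an observed bilateral one. For general missing data the source is too wide, and under the Protocol wording it extends to the preoperative reply.

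Each changed score moves the rate by 1.25 points, assuming 80 analysed subjects. How many scores would change is unknown. The ranges above rest on assumed rates, and few cases are expected.

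A reader might infer that the rule biases the rate upward, or that one extra event would fail the study because the upper limit passes 10%. Neither is supported. The bias can go either way. SAP 4.1 states that the aim is to estimate the rate, the clinical hypothesis names no confidence limit, and the point estimate of 3.75% is still below 10%. The 2/80 and 3/80 intervals illustrate sensitivity and do not cross a decision boundary.

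**What to change.** In SAP 2.1 and Protocol 20.2, in the same words:

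1. For the bilateral primary endpoint, only a questionnaire completed after the second-eye implant may be carried forward for a missing 6-month reply. Subjects with no such reply go to the planned multiple imputation and the best-case and worst-case analyses. The SAP's condition for imputation, no questionnaire at any time point, needs the same qualifier.
2. For subjects repositioned before the second implant and later implanted bilaterally, report the primary rate both ways: with the pre-procedure or default-severe score, and with the observed 6-month bilateral reply. Name the headline before the replies are seen. Say whether the preoperative questionnaire counts as data before the procedure.
3. List these subjects with surgery, questionnaire and procedure dates and both replies.

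Cost: a few sentences in each document, one extra result row, one listing, and possibly a few more subjects sent to imputation. Surgery dates are on the operative form and visit dates are in the source records. No visit, procedure or treatment changes.
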